≥ 3 (clinical TLS)	N/A	TLS should be managed according to the local standard of care and institutional guidelines	
 • N/A 	Immediately stop the infusion (if applicable) and permanently discontinue AMG 160

Abbreviations and footnotes defined on last page of table.

Table 6-3. Infusion Interruptions/Delays/Withholding/Permanent Discontinuation and Management of Adverse Events Including Dose Reductions

Grade	Interruption/Delay	Specific Management	Re-start guidance	Permanent Discontinuation
Neurological events related to AMG 160				
≥ 2	Interruption/ delay until event has improved to grade ≤ 1	
For CRS-related neurological events, use ICANS grading and management system
 
Consider administration of corticosteroids (and tocilizumab^{c,d,e} if associated with CRS).
 
Following a seizure: administer anti-seizure medication according to the local standard of care and institutional guidelines
 
For grade ≥3 events, contrast-enhanced magnetic resonance imaging (MRI) of the head should be performed. A neurology consult is recommended.
	
 • Re-start possible if successfully managed and improvement to ≤ grade 1 in ≤ 14 days. • In case of infusion interruption, continue treatment with next scheduled infusion (do not resume prior infusion). • Delay of next infusion: 
 – < 7 days: administer the delayed infusion (as long as the next scheduled infusion is > 6 days from delayed infusion) and follow the schedule of assessments for the cycle day on which the infusion was originally planned. – > 7 days: skip the infusion and resume schedule of assessments for the next scheduled infusion • Hospitalization: 48 hours • Dose modification: resume at the same dose or reduce to next lower dose if clinically indicated • Additional measures: ██████████ and additional assessments as indicated in Section 6.2.2.1.2.4 	
If grade 4 event
 
OR
 
In case of more than 1 seizure
 
OR
 
If resolution or improvement to ≤ grade 1 in > 14 days
 
OR
 
In case of repeat ≥ grade 2 event despite dose reduction

Abbreviations and footnotes defined on last page of table.

Table 6-3. Infusion Interruptions/Delays/Withholding/Permanent Discontinuation and Management of Adverse Events Including Dose Reductions

Grade	Interruption/Delay	Specific Management	Re-start guidance	Permanent Discontinuation
Gastrointestinal events related to AMG 160				
2	Interruption/ delay required if deemed intolerable by the subject or investigator and not responding to appropriate medical management until event has improved to grade ≤ 1	GI toxicities should be managed according to the local standard of care and institutional guidelines	
 • Re-start possible if successfully managed and improvement to \leq grade 1 in ≤ 14 days. • In case of infusion interruption, continue treatment with next scheduled infusion (do not resume prior infusion). • Delay of next infusion: 
 – < 7 days: administer the delayed infusion (as long as the next scheduled infusion is > 6 days from delayed infusion) and follow the schedule of assessments for the cycle day on which the infusion was originally planned. – > 7 days: skip the infusion and resume schedule of assessments for the next scheduled infusion • Hospitalization: 48 hours • Dose modification: resume at the same dose or reduce to next lower dose if clinically indicated • Additional measures: [REDACTED] and additional assessments as indicated in Section 6.2.2.1.2.4 	If subject missed more than 2 consecutive doses of AMG 160

Abbreviations and footnotes defined on last page of table.

Table 6-3. Infusion Interruptions/Delays/Withholding/Permanent Discontinuation and Management of Adverse Events Including Dose Reductions

Grade	Interruption/Delay	Specific Management	Re-start guidance	Permanent Discontinuation
Gastrointestinal events related to AMG 160 (continued)				
≥ 3	Interruption/ delay until event has improved to grade ≤ 1	GI toxicities should be managed according the local standard of care and institutional guidelines	
 • Re-start possible if successfully managed and improvement to ≤ grade 1 in ≤ 14 days. • In case of infusion interruption, continue treatment with next scheduled infusion (do not resume prior infusion). • Delay of next infusion: 
 – < 7 days: administer the delayed infusion (as long as the next scheduled infusion is > 6 days from delayed infusion) and follow the schedule of assessments for the cycle day on which the infusion was originally planned. – > 7 days: skip the infusion and resume schedule of assessments for the next scheduled infusion • Hospitalization: 48 hours • Dose modification: resume at the same dose or reduce to next lower dose if clinically indicated • Additional measures: ██████████ and additional assessments as indicated in Section 6.2.2.1.2.4 	
If subject missed more than 2 consecutive doses of AMG 160
 
OR
 
In case of reappearance of same event at grade 4
 
OR
 
In case of repeat grade ≥ 3 event despite dose reduction

Abbreviations and footnotes defined on last page of table.

Table 6-3. Infusion Interruptions/Delays/Withholding/Permanent Discontinuation and Management of Adverse Events Including Dose Reductions

Grade	Interruption/Delay	Specific Management	Re-start guidance	Permanent Discontinuation
Any other AMG 160-related events not meeting DLT criteria				
≥ 3	Interruption/ delay required if deemed intolerable and/or clinically significant by the subject or investigator and not responding to appropriate medical management until event has improved to grade ≤ 1		
 • Re-start possible if successfully managed and improvement to ≤ grade 1 in ≤ 14 days. • In case of infusion interruption, continue treatment with next scheduled infusion (do not resume prior infusion). • Delay of next infusion: 
 – < 7 days: administer the delayed infusion (as long as the next scheduled infusion is > 6 days from delayed infusion) and follow the schedule of assessments for the cycle day on which the infusion was originally planned. – > 7 days: skip the infusion and resume schedule of assessments for the next scheduled infusion • Hospitalization: 48 hours • Dose modification: resume at the same dose or reduce to next lower dose if clinically indicated • Additional measures: ██████████ and additional assessments as indicated in Section 6.2.2.1.2.4 	If subject missed more than 2 consecutive doses of AMG 160 OR In case of reappearance of same event at grade 4 OR In case of repeat grade ≥ 3 event despite dose reduction

Abbreviations and footnotes defined on last page of table.

Table 6-3. Infusion Interruptions/Delays/Withholding/Permanent Discontinuation and Management of Adverse Events Including Dose Reductions

Grade	Interruption/Delay	Specific Management	Re-start guidance	Permanent Discontinuation
Any Non-AMG 160-related events				
4	Interruption/ delay required if deemed intolerable by the subject or investigator and not responding to appropriate medical management until event has improved to grade \leq 1		
 • Re-start possible if successfully managed and improvement to \leq grade 1 in \leq 28 days. • In case of infusion interruption, continue treatment with next scheduled infusion (do not resume prior infusion). • Delay of next infusion: 
 – < 7 days: administer the delayed infusion (as long as the next scheduled infusion is > 6 days from delayed infusion) and follow the schedule of assessments for the cycle day on which the infusion was originally planned. – > 7 days: skip the infusion and resume schedule of assessments for the next scheduled infusion • Hospitalization: 48 hours • Dose modification: resume at the same dose or reduce to next lower dose if clinically indicated • Additional measures: [REDACTED] and additional assessments as indicated in Section 6.2.2.1.2.4 	If subject missed more than 2 consecutive doses of AMG 160 OR In case of reappearance of same event at grade 4

Abbreviations and footnotes defined on last page of table.

Table 6-3. Infusion Interruptions/Delays/Withholding/Permanent Discontinuation and Management of Adverse Events Including Dose Reductions

Grade	Interruption/ Delay	Specific Management	Re-start guidance	Permanent Discontinuation
[Redacted]				
Hepatotoxicity				
For Stopping and Rechallenge Rules please refer to Section 11.7 .				
[Redacted]				

Abbreviations and footnotes defined on last page of table.

Table 6-3. Infusion Interruptions/Delays/Withholding/Permanent Discontinuation and Management of Adverse Events Including Dose Reductions

SARS CoV2 infection and COVID19 disease				
asymptomatic	
Interruption required until at least 10 days since positive SARS-CoV-2 test.
 
UNLESS patient previously fully vaccinated against SARS-CoV-2. If patient previously vaccinated and tests positive, then discuss with Medical Monitor.
	
Follow local guidelines and standard of care for COVID-19 treatment and isolation
 
Contact Amgen Medical Monitor within 1 business day to ensure appropriate documentation & management of study activities
	
 • Re-start possible upon agreement between Investigator and Amgen Medical Monitor provided: 
 ○ There are no new findings on physical exam related to SARS-CoV-2, AND ○ Subject tests negative for SARS-CoV-2 by RT-PCR, OR 
 ○ If subject continues to test positive for SARS-CoV-2 more than 10 days after initial positive test, or If subject initially tests positive in the setting of prior COVID vaccination, resume IP only after discussion with patient and reassessment of individual risk/benefit • Consider chest imaging, ECG, ECHO, and cardiology assessment prior to re-start • Consider hospitalization for re-start of IP based on length of treatment interruption, risk of CRS at restart, and amount of time since patient was last treated • Dose modification: resume at the same dose or reduce to next lower dose if clinically indicated • ██████████ and assessments: follow guidance in Section 1.3 	
Immediately stop the infusion (if applicable) and permanently discontinue IP therapy, if:
 
Subject required treatment interruption greater than 28 days and upon discussion with Amgen Medical Monitor the decision is made to permanently discontinue treatment
 
OR
 
Initial benefit/risk assessment for individual patient is not maintained any longer

Abbreviations and footnotes defined on last page of table.

Table 6-3. Infusion Interruptions/Delays/Withholding/Permanent Discontinuation and Management of Adverse Events Including Dose Reductions

Grade	Interruption/ Delay	Specific Management	Re-start guidance	Permanent Discontinuation
SARS CoV2 infection and COVID19 disease (continued)				
symptomatic	Interruption required until at least 10 days since complete resolution of acute symptoms	Follow local guidelines and standard of care for COVID-19 treatment and isolation Contact Amgen Medical Monitor within 1 business day to ensure appropriate documentation & management of study activities	
 Re-start possible upon agreement between Investigator and Amgen Medical Monitor provided: 
 There are no new findings on physical exam and chest imaging, related to SARS-CoV-2 Subject tests negative for SARS-CoV-2 by RT-PCR, OR 
 If subject continues to test positive for SARS-CoV-2 more than 10 days after initial positive test, resume IP only after discussion with patient and reassessment of individual risk/benefit Consider chest imaging, ECG, ECHO, and cardiology assessment prior to re-start Consider hospitalization for re-start of IP based on length of treatment interruption, risk of CRS at restart, and amount of time since patient was last treated Dose modification: resume at the same dose or reduce to next lower dose if clinically indicated ██████████ and assessments: follow guidance in Section 1.3 	Immediately stop the infusion (if applicable) and permanently discontinue IP therapy if: Subject required treatment interruption greater than 28 days due to severe or life-threatening COVID-19 OR Initial benefit/risk assessment for individual patient is not maintained any longer

CRS = cytokine release syndrome; COVID-19 = coronavirus disease 2019; CTCAE = Common Terminology Criteria for Adverse Events; ECG = electrocardiogram; ECHO = echocardiogram; GI = gastrointestinal; ICANS = immune-effector cell associated neurologic syndrome; IL-6 = interleukin 6; IP = investigational product; IV = intravenous; MRI = magnetic resonance imaging; N/A = not applicable; NSAIDS = non-steroidal anti-inflammatory drugs; PK = pharmacokinetics; Q2 = every 2; RT-PCR = real time polymerase chain reaction; SARS-CoV-2 = severe acute respiratory syndrome coronavirus 2; TLS = tumor lysis syndrome; US = United States

^a Revised grading system for CRS (Lee et al, 2014)

^b High dose vasopressors (all doses are required for ≥ 3 hours): Norepinephrine monotherapy ≥ 20 µg/min; Dopamine monotherapy ≥ 10 µg/kg/min, Phenylephrine monotherapy ≥ 200 µg/min, Epinephrine monotherapy ≥ 10 µg/min; If on vasopressin, vasopressin + norepinephrine equivalent of ≥ 10 µg/min; If on combination vasopressors (not vasopressin), norepinephrine equivalent of ≥ 20 µg/min

- ^c All sites will ensure that CRS rescue medications are available on-site, including corticosteroids and (for sites in regions where tocilizumab is approved and available, eg, the US and Germany) 2 doses of tocilizumab per study subject
- ^d If tocilizumab is not available, siltuximab (an anti-IL-6 monoclonal antibody) may be used in the management of cytokine release syndrome, following the criteria outlined in the Management of Adverse Events table. The recommended dose of siltuximab is 11 mg/kg administered over 1 hour as an intravenous infusion, consistent with the prescribing information for the treatment of multicentric Castleman's disease (Sylvant Prescribing Information), and the CARTOX Working Group Guidelines for CRS management (Neelapu, 2018). Siltuximab may be repeated if needed, in the event that CRS recurs after a subsequent infusion of AMG 160. Siltuximab may not be repeated in an individual subject that develops anaphylaxis to siltuximab, or gastrointestinal perforation after siltuximab.
- ^e A subgroup analysis for subjects treated with siltuximab will be evaluated, including CRS outcomes, safety, and PK data.

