6.2.2 Dosage Adjustments, Delays, Rules for Withholding or Restarting, Permanent Discontinuation

6.2.2.1 Amgen Investigational Product: AMG 160

The reason for dose change of AMG 160 is to be recorded on each subject's electronic case report form (eCRF).

For treatment interruptions, delays, and discontinuations, refer to AMG 160 guidance in [Table 6-3](#) in consultation with the Amgen medical monitor.

If any of the following events occur, further accrual will be suspended and a safety analysis conducted and submitted to FDA for review prior to resuming enrollment.

- any 1 treatment-related grade 5 adverse event or
- any 2 of the same treatment-related, clinically significant grade 4 adverse events at least possibly related to AMG 160

6.2.2.1.1 Infusion Interruptions/Delays/Withholding and Re-start in Case of Technical/Logistical Issues

Events leading to infusion interruption or delay for technical/logistical reasons may include: technical problem with the infusion pump or the investigational product is incorrectly prepared or administered.

Infusion Interruptions due to Technical/Logistical Issues

The administration of AMG 160 should not be interrupted for short-term (approximately 60 minute) or [REDACTED], if possible. In case of infusion interruption, due to any technical or logistic reason, the interruption should be as short as possible and the infusion continued at the earliest time possible.

[figure not shown]
In case of infusion interruption, immediately consult with Amgen medical monitor to determine if:

- investigational product stability is sufficient to administer the remaining infusion or
- a new infusion can be administered or
- the dose should be withheld

For short-term (approximately 60 minute) infusions, if the remaining infusion can be administered, no specific precautions have to be taken. If a new infusion can be administered, follow the procedures in the Schedule of Activities (see Section 1.3) or the cycle day on which the original (interrupted) infusion was administered. [REDACTED]

[REDACTED] If the

infusion will need to be withheld, follow the instructions for re-start after interruptions due to adverse events described below for the next infusion.

Any interruption of an infusion should be recorded in the eCRF, providing the start and stop date/time of the infusion if the interruption is > 2 hours.

Infusion Delay due to Technical/Logistical Issues

[figure not shown]

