6.2.2.1.2 Infusion Interruptions/Delays/Withholding and Re-start due to Adverse Events

6.2.2.1.2.1 General Guidelines

Subjects should be assessed for toxicity before each infusion of AMG 160. The severity of the toxicity will be graded using the CTCAE version 5.0, with the exception of CRS, which must be graded using the criteria referenced in the publication by Lee et al, 2014; TLS, which must be graded according to the Cairo Bishop criteria referenced in the publication by Coiffier et al, 2008; and immune-effector cell associated neurologic syndrome (ICANS) will be using the criteria referenced in the publication by Lee et al, 2019. Infusion modification and dose reduction due to a toxicity will be performed according to the instructions described below and outlined in [Table 6-3](#).

6.2.2.1.2.2 Infusion Interruptions due to Adverse Events

Events occurring during the infusion and requiring treatment interruption will be managed by immediate infusion interruption. The site should record any unscheduled interruption of an infusion on the eCRF and provide the start and stop date/time of the infusion.

Events requiring an infusion interruption are listed in [Table 6-3](#).

6.2.2.1.2.3 Delay of Subsequent Infusion due to Adverse Events

Events occurring after the end of the infusion and requiring a delay of treatment will be managed by delay of the subsequent infusion. The site should record any delay of an infusion on the eCRF and provide the start and stop date/time of the infusion.

Events requiring a delay of the subsequent infusion are listed in [Table 6-3](#).

Infusion interruptions or delays for other reasons need to be discussed with the Amgen medical monitor.

6.2.2.1.2.4 Re-start of Infusion

Re-starting treatment after an interruption/delay due to an adverse event or if the interruption/ delay was > 72 hours, regardless of the reason, should be performed under medical supervision. [REDACTED]

[REDACTED]. The following assessments should be performed as for days 1, 2, and 3 per the Schedule of Activities for cycle 1 (see Section [1.3](#)).

- vital signs, pulse oximetry
- physical examination
- neurological examination (only in case the treatment interruption was due to a neurologic event)
- weight
- ECOG
- safety labs (hematology, chemistry, coagulation, urinalysis)

The subject should be hospitalized for at least 48 hours after re-start of the infusion.

6.2.2.1.2.5 Dose Adjustments and Re-start at a Lower Dose Level

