For adverse events for which restart of treatment is allowed according to the guidelines outlined in [Table 6-3](#), treatment may be resumed at the same or lower dose.

Re-start at a lower dose level:

In the following cases, the next infusion administered should be at the previous (lower) dose level:

If the event occurred during the infusion and caused an interruption of the infusion for more than 72 hours and therefore the affected dose was withheld, or

If the event started after the end of an infusion and administration of the next infusion had to be delayed for more than 72 hours due to the event.

For specific events as outlined in [Table 6-3](#).

[figure not shown]

In either case, re-escalation to the target dose can be considered for the next infusion if treatment at the lower dose has been well tolerated with no events requiring dose interruption or delay as described in [Table 6-3](#). After the dose re-escalation, the following assessments should be performed as for day 8 through day 11 per the Schedule of Activities for cycle 1 (see Section [1.3](#)).

- vital signs, pulse oximetry
- physical examination
- neurological examination (only in case the treatment interruption was due to a neurologic event)
- safety labs (hematology, chemistry, coagulation, urinalysis)

The subject should be hospitalized for at least 48 hours after re-escalation.

In case an additional dose de-escalation is required, permanently discontinue treatment.

Table 6-3. Infusion Interruptions/Delays/Withholding/Permanent Discontinuation and Management of Adverse Events Including Dose Reductions

Grade	Description of Severity	Interruption/Delay	Specific Management	Re-start guidance	Permanent Discontinuation
Infusion-related Reaction					
1	Mild transient reaction; infusion interruption not indicated; intervention not indicated	N/A	Consider medication to control infusion reaction as deemed appropriate by the investigator according to local standard of care and institutional guidelines.	N/A	N/A

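### Six AMG 160-related re-start cells in Protocol Table 6-3 leave the same dose open after a delay of more than 72 hours, where Section 6.2.2.1.2.5 calls for the lower dose

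*Protocol*

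**What the plan says.** Protocol Section 6.2.2.1.2.5 opens with a default for events where Table 6-3 allows re-start: "treatment may be resumed at the same or lower dose". It then restricts that default: "In the following cases, the next infusion administered should be at the previous (lower) dose level". Three cases follow:

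- the event interrupted an infusion for more than 72 hours and the dose was withheld;
- the event began once an infusion was over, with the result that "administration of the next infusion had to be delayed for more than 72 hours due to the event";
- the event is one that Table 6-3 itself singles out for a reduction.

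The table-specific reductions are therefore listed in addition to the 72-hour cases and do not replace them. After a well-tolerated lower dose, "re-escalation to the target dose can be considered for the next infusion".

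Two sentences say how text and table are to be used. Section 6.2.2.1: "For treatment interruptions, delays, and discontinuations, refer to AMG 160 guidance in" Table 6-3, "in consultation with the Amgen medical monitor". Section 6.2.2.1.2.1: "Infusion modification and dose reduction due to a toxicity will be performed according to the instructions described below and outlined in" Table 6-3.

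In Table 6-3, the dose line of six AMG 160-related re-start cells allows either the same dose or a reduction on clinical grounds. These are infusion reaction grade 2, CRS grade 2, neurological grade 2 or higher, GI grade 2, GI grade 3 or higher, and other related grade 3 or higher. Each cell splits delays at 7 days to decide whether the late infusion is given or skipped, and each refers to Section 6.2.2.1.2.4 for added assessments. No readable text in these cells or in the table footnotes mentions 72 hours in connection with dose, or cites Section 6.2.2.1.2.5.

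**The concern.** The section ties the lower dose to how long the event held up treatment. The six cells turn the same decision into clinical discretion with no limit on duration. A site that takes the dose from the cell could give the full dose of a T-cell engager to a subject whose toxicity resolved slowly, when the text calls for one level lower.

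The choice also affects later decisions. In the neurological, GI grade 3 or higher and other related rows, a repeat event after a dose reduction requires permanent discontinuation. Section 6.2.2.1.2.5 also stops treatment when a further de-escalation is needed. If the first reduction is missed, neither criterion comes into play, so two subjects with the same course could be handled differently depending on which page the site used.

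**Working it through.** The plan states no figure here to reproduce. The check compares the two texts and then finds when they diverge.

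**Step 1: text against cell, by length of delay.**

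| Delay of next infusion | Section 6.2.2.1.2.5 | Six cells, two-weekly dosing |
|---|---|---|
| up to 72 h | same or lower dose | give infusion; same or lower dose |
| over 72 h, under 7 days | lower dose | give infusion; same or lower dose |
| over 7 days | lower dose | skip, resume at next scheduled infusion; same or lower dose |

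The second and third lines diverge. A skip after more than 7 days (168 h) always exceeds 72 h.

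**Step 2: when the delay case arises.** Let o be onset in days after the last infusion, r days to grade 1 or better, and I the dosing interval. I = 14 once the target dose is reached; I = 7 for the weekly cycle 1 infusions in Tables 1-2 and 1-3. Assume the infusion is given as soon as the event has improved.

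Delay = o + r − I, which exceeds 3 days when o + r > I + 3. That is 17 on two-weekly dosing and 10 on weekly dosing.

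**Step 3: apply each row's recovery limit from Table 6-3.**

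| Row | Limit on r | Two-weekly | Weekly |
|---|---|---|---|
| Neurological ≥ 2, GI 2, GI ≥ 3, other related ≥ 3 | 14 days | onset after day 17 − 14 = 3 | 10 − 14 = −4, so any onset |
| CRS 2 | 7 days | onset after day 17 − 7 = 10 | onset after day 10 − 7 = 3 |
| Infusion reaction 2, o = 0 | 14 days | longest delay 0 + 14 − 14 = 0 days, so none | longest delay 0 + 14 − 7 = 7 days; needs r > 10 |

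The onset limits are outer edges, reached only when recovery takes nearly the full time allowed. Appendix 10 (Section 11.10.1) places increased CRS risk in the first few days after dosing, so overlap in the CRS grade 2 row should be uncommon.

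**Step 4: does the table direct the late infusion to be given?** Its proviso is that the next scheduled infusion must be more than 6 days away. On two-weekly dosing, a delay of 3 to 7 days leaves 14 − 3 = 11 down to 14 − 7 = 7 days, so the proviso is met. On weekly dosing, a delay over 3 days leaves less than 7 − 3 = 4 days, so the proviso fails and the same-dose option passes to a later scheduled infusion.

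**Example.** On two-weekly dosing, a related grade 2 neurological event starts on day 6 and improves to grade 1 on day 18. Then r = 12 (limit 14) and the delay is 18 − 14 = 4 days. The next scheduled infusion is 28 − 18 = 10 days away. The cell says to give the infusion and offers the same dose; the section calls for the lower dose.

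**Interruption case.** This needs an event that starts during the infusion and holds it up for more than 72 hours. The six cells say not to resume an interrupted infusion, again with no dose condition. With infusions of about 60 minutes this should be infrequent, and a grade 2 infusion reaction is by its table description one that responds promptly.

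**Analysis.** DLT incidence and objective response are tabulated by planned dose level (Protocol Sections 9.4.2.3.1 and 9.4.2.2), so a one-level change in a given dose moves neither.

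**The case against.** The strongest reply is that nothing conflicts. The six cells repeat the section's own default, the restriction is printed just before the table, and Section 6.2.2.1.2.1 makes text and table apply together to dose reduction. The instruction in Section 6.2.2.1 that sends sites to the table concerns interruptions, delays and discontinuations rather than dose, and it requires medical-monitor consultation; CRS grade 2 repeats that requirement in its own cell. All six cells cite Section 6.2.2.1.2.4, which itself uses a 72-hour threshold and directly precedes the dose rule. Re-start also needs recovery to grade 1 or better and 48 hours in hospital, the rule says should, and re-escalation may follow at the next infusion.

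Most of this stands, and it settles which instruction governs. A reader might infer that the protocol contradicts itself. It does not: no cell requires the same dose, and reducing satisfies both texts. What remains is that the cell, where the dose is looked up, permits a choice that the section advises against and gives no sign of the limit.

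Two further readings go too far. The unrelated grade 4 row and the two SARS-CoV-2 rows carry the same dose line, so a reader might count nine rows. The section's wording does not exclude them, but nothing shows that the sponsor meant a rule for slow-resolving toxicity to cover events not attributed to AMG 160. The SARS-CoV-2 rows also need medical-monitor agreement, and their 10-day wait delays a two-weekly infusion by more than 72 hours only if counted from more than 17 − 10 = 7 days after the last infusion. A reader might also object that the GI grade 3 or higher row allows re-start after a first grade 4 event. That concerns the discontinuation column, not the 72-hour rule.

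**Conclusion.** The concern holds for six AMG 160-related cells of Table 6-3. Section 6.2.2.1.2.5 governs, but the cells leave the same-dose option open for delays of 3 to 7 days and over 7 days without pointing to it. In practice it mainly concerns four rows: neurological, GI grade 2, GI grade 3 or higher, and other related. There, on two-weekly dosing, it needs recovery later than day 17 after the last infusion. The difference is one dose level, possibly for a single infusion, plus its effect on the later discontinuation criteria. It is a safety-consistency point worth correcting, and no statistical figure depends on it.

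The conclusion assumes that the blacked-out text does not supply the missing pointer. The dose lines of all six cells are readable, but parts of their added-measures entries, part of Section 6.2.2.1.2.4, and a figure after the list of lower-dose cases in Section 6.2.2.1.2.5 cannot be seen.

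**What to change.** Add to the dose line of each of the six cells: *if the event-related interruption/delay was > 72 hours, the next infusion should be at the next lower dose (Section 6.2.2.1.2.5)*. Keep the word should, so that the rule is no stricter than the sponsor wrote it.

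Add one sentence to Section 6.2.2.1.2.5: the 72-hour rule limits the same-dose option in Table 6-3, and the existing grade 3 CRS option to continue at the same dose after medical-monitor consultation is kept.

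The cost is wording in six cells and one sentence. The downside is slightly more one-level reductions, which bring the repeat-event-after-reduction and second-de-escalation stopping criteria into play for those subjects. Sample size, visits and analyses stay as they are. The descriptive count of dose modifications in SAP Section 9.6.8 would reflect any added reductions.
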